6.13.6. Vital Signs and Other Physical Findings

Vital sign data including blood pressure (BP), pulse rate (PR), temperature (T), height and weight will be summarized for all patients on therapy. Patients with abnormal vital signs will be summarized.

6.13.7. Electrocardiograms

For each patient, 12-lead ECGs will be obtained according to the Study Schedule (Protocol Attachment 1). All ECGs will be analyzed for safety and categorical analysis will be provided including:

1. Number and percentage of individuals with abnormal ECG findings.
2. Number and percentage of individuals with AEs that could be associated with prolongation of cardiac repolarization or proarrhythmia, for example, palpitations, dizziness, syncope, cardiac arrhythmias and sudden death.

Categorical analysis of the following ECG parameter may be performed at day 1 and day 15 of each cycle and the short term follow up visit at the time points outlined in the protocol and changes will be compared to baseline (that is, Cycle 1, Day 1 pre-dose). Such analysis will be triggered only as needed. If triggered, the analysis will include the number and percentage of individuals with:

1. Absolute QT/QTc values >450 ms, >480 ms, and >500 ms; as well as the number and percentage of individuals with change from baseline >30 ms and >60 ms.
2. PR changes from baseline $\geq 50\%$ if baseline value is <200 ms and $\geq 25\%$ of baseline value is ≥ 200 ms.
3. QRS changes from baseline $\geq 50\%$ if baseline value is <110 ms and $\geq 25\%$ of baseline value is ≥ 110 ms.

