6.1.2. Exclusion Criteria

Potential study patients may not be included in the study if any of the following apply during screening.

- [11] Have received treatment within 28 days of the initial dose of study drug with an investigational product or non-approved use of a drug or device (other than the study drug/device used in this study) for non-cancer indications or are concurrently enrolled in any other type of medical research judged not to be scientifically or medically compatible with this study.
- [12] Have serious preexisting medical conditions or concomitant disorders that, in the opinion of the investigator, would exclude the patient as a candidate for this study.

- [13] Have active central nervous system (CNS) or leptomeningeal metastasis (brain metastasis) at the time of study entry. Patients with a history of a CNS metastasis previously treated with curative intent (eg, stereotactic radiation or surgery) that have not progressed on follow-up imaging, have been asymptomatic for at least 28 days and are not receiving corticosteroids and/or anticonvulsants, are eligible. Patients with signs or symptoms of neurological compromise should have appropriate radiographic imaging performed before study entry to rule out brain metastasis.
- [14] Have current acute or chronic leukemia.
- [15] Have an active symptomatic fungal, bacterial, and/or known viral infection including human immunodeficiency virus (HIV) or viral (A, B, or C) hepatitis (screening is not required).
- [16] Have a second primary malignancy that, in the judgment of the investigator or Sponsor, may affect the interpretation of results.
- [17] Have Bazett's corrected QT interval (QTc) of >470 msec on screening electrocardiogram (ECG) in repeated measurements.
Note: Patients with permanent pacemakers may enter study if QTc is >470 msec if measured from a paced conduction and not an intrinsic (non-paced beat) conduction.
- [18] Have a serious cardiac condition, such as congestive heart failure; New York Heart Association Class III/IV heart disease; unstable angina pectoris; myocardial infarction within the last 3 months; valvulopathy that is severe, moderate, or deemed clinically significant; or arrhythmias that are symptomatic or require treatment (not including patients with rate-controlled atrial fibrillation).

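### SAP 6.13.7's optional QTc threshold counts set no condition on baseline, and their Day 1/15 visits miss most Cycle 1 ECG time points on weekly Schedule 2

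*SAP*

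**What the plan says.** Protocol 6.1.2, exclusion [17], removes patients who "Have Bazett's corrected QT interval (QTc) of >470 msec on screening electrocardiogram (ECG) in repeated measurements". Its Note adds that "Patients with permanent pacemakers may enter study if QTc is >470 msec if measured from a paced conduction", with no upper limit for them.

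SAP 6.13.7 commits to two ECG summaries drawn from all ECGs: abnormal findings, and adverse events that could reflect delayed repolarization or proarrhythmia. It then describes a further categorical analysis that "may be performed at day 1 and day 15 of each cycle and the short term follow up visit", with the qualifier "Such analysis will be triggered only as needed". If run, its first item counts individuals with "Absolute QT/QTc values >450 ms, >480 ms, and >500 ms" and also the "number and percentage of individuals with change from baseline >30 ms and >60 ms". Baseline is the Cycle 1 Day 1 predose ECG. The PR and QRS items in the same list are changes from baseline with cut-offs that depend on the baseline value. The QTc correction is not named.

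SAP 5.1 describes dosing on Days 1 and 15 only. Protocol 6.2 now has two schedules: Days 1 and 15 (Schedule 1) and Days 1, 8, 15 and 22 (Schedule 2). Protocol Attachment 4 schedules Cycle 1 ECGs on Days 1, 2, 3, 8, 15 and 22 for both.

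**The concern.** A count of patients above an absolute QTc value is normally read as something that happened on treatment. Here a patient can satisfy the lowest threshold on the value that admitted them to the study, and a paced patient can satisfy all three. Dose levels hold from 3 to 20 patients, so one such patient moves a row by between 1/20 = 5 and 1/3 = 33 percentage points.

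The visit rule raises a second problem. Under weekly dosing, Days 1 and 15 are only half of the dosing days. In Cycle 1 the ECGs at 24 and 48 hours after the first infusion and those around the second weekly dose fall outside the interval counts. If a QT question arose on Schedule 2, the analysis written to answer it would leave out most of the Cycle 1 time points collected.

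**Working it through.** **Inputs.** Entry limits are from Protocol 6.1.2 [17] and its Note. Thresholds and visit days are from SAP 6.13.7. ECG time points are from Protocol Attachment 4 and, as a variant, the Central ECG comment in Attachment 1. The planned total of about 50 patients is from Protocol 6.2. The plan gives no figure for the ECG analysis, so there is none to reproduce.

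**Step 1: entry range against thresholds.** This assumes that the SAP's QTc uses the same correction as entry.

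- Unpaced, screening QTc 451 to 470 ms: above 450 ms, but not above 480 or 500 ms, because 470 < 480. Only the >450 row overlaps.
- Paced: no upper limit at entry, so any of the three rows can be met before treatment.

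**Step 2: do the change counts resolve this?** Take two patients. The first has 460 ms at baseline and throughout: change 460 − 460 = 0. The second goes from 450 to 460 ms: change 460 − 450 = 10 ms. Both are in the >450 row and neither is in the >30 or >60 row, yet only the second crossed the threshold on study. The change counts show large shifts, but not which members of an absolute row were there at baseline.

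**Step 3: Cycle 1 coverage.** Post-baseline time points, excluding the Day 1 predose ECG:

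| Day | Schedule 1 (Att. 4) | Schedule 2 (Att. 4) | Schedule 2 (Att. 1 comment) |
|---|---|---|---|
| 1 | 3 | 3 | 3 |
| 2 | 1 | 1 | 1 |
| 3 | 1 | 1 | 1 |
| 8 | 1 | 4 | 4 |
| 15 | 4 | 1 | 4 |
| 22 | 1 | 1 | 4 |
| Total | 11 | 11 | 17 |
| Days 1 + 15 | 7 | 4 | 7 |
| Omitted | 4 (36%) | 7 (64%) | 10 (59%) |

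The two Schedule 2 columns differ because Attachment 4 has a single predose ECG on Days 15 and 22 of Cycle 1, while the Attachment 1 comment calls for a triplicate predose, end-of-infusion, 2-hour and 6-hour series on every Cycle 1 dosing day. Day 8 has that full series under both, and the SAP rule omits it under both. From Cycle 2, Attachment 4 has four predose ECGs per cycle on Schedule 2, of which two (Days 8 and 22) are omitted.

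**Step 4: possible size of the overlap.** The documents do not say how many patients enter above 450 ms. For an assumed proportion q, the expected number among 50 is 50q, and the chance of at least one in a 10-patient dose level is 1 − (1 − q)^10.

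| q (assumed) | Expected of 50 | At least one of 10 |
|---|---|---|
| 2% | 1 | 18% |
| 5% | 2.5 | 40% |
| 10% | 5 | 65% |
| 20% | 10 | 89% |

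These figures illustrate scale only.

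**The case against.** The strongest reply is that this is a conditional, descriptive table with safeguards around it. The interval analysis may never run. All ECGs are analyzed for abnormal findings, so the Day 2, 3, 8 and 22 recordings are not lost to safety review. The item that lists the absolute values also lists the >30 and >60 ms changes, so a patient with a long but stable QTc appears in no change row. For unpaced patients only the lowest threshold overlaps entry. The number of paced patients is unknown, and exclusion [18] removes many patients with serious cardiac disease. The Schedule 2 gap arises because the SAP was written for Days 1 and 15 dosing.

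All of this is correct and limits the importance of the point. It does not remove it. No trigger criterion is given, and if a QT question arises this is the interval analysis the SAP provides. The change counts leave the absolute rows ambiguous (Step 2 of the working). An outdated visit list still gives the wrong coverage if it is followed.

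Four stronger readings are tempting and are not supported:

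- A reader might infer that these rows are the trial's main QT result. The SAP makes them optional and commits only to the abnormal-findings and adverse-event summaries.
- A reader might infer that the ECGs on the other days are discarded. They are absent only from the interval counts.
- A reader might infer that the >480 and >500 ms rows are generally inflated by the entry rule. That route is open only to paced patients.
- A reader might infer that Day 8 holds the only triplicates around a repeat dose on Schedule 2. That is so under Attachment 4 but not under the Attachment 1 comment. SAP 6.13.7 cites Attachment 1, while Protocol 8.1.3.1 cites both.

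**Conclusion.** The point holds within these limits. If the optional analysis is triggered, the >450 ms row can include unpaced patients with no change on drug, and any row can include paced patients whose value was already high. On coverage, the Day 1/15 rule omits 7 of 11 post-baseline Cycle 1 time points on Schedule 2 under Attachment 4 (10 of 17 under the Attachment 1 comment) and 4 of 11 on Schedule 1. The Schedule 2 majority holds under either attachment.

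The overlap conclusion assumes the same correction at entry and on study. Entry names Bazett and the SAP names none, so a mismatch is possible but not shown. The number of patients affected cannot be derived from the documents. The coverage counts are exact for the schedules as written. This is an inexpensive improvement to a secondary safety table, and nothing here suggests that the committed ECG summaries are wrong.

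**What to change.** In SAP 6.13.7:

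1. Count a patient at each absolute threshold only when baseline is at or below it and a post-baseline value is above it, or give a shift table of baseline category by worst post-baseline category. Keep the >30 and >60 ms change counts.
2. Define baseline as the mean of the Cycle 1 Day 1 predose triplicate. SAP Table JNBA.6.1 already permits averaging of predose measures.
3. Present paced ECGs separately from the QTc counts.
4. Replace Days 1 and 15 with every protocol-scheduled ECG day for each schedule, and keep the follow-up visit.
5. Name the QT correction and include Bazett, as used at entry.

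Separately, Protocol Attachments 1 and 4 disagree on the Cycle 1 Day 15 and Day 22 ECGs for Schedule 2 and must be reconciled.

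The analysis changes use ECGs already scheduled and need only SAP wording and minor programming. The downside is a slightly longer table.

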6.14. Protocol Violations

All significant protocol deviations will be summarized by cohorts and by reasons (for example, inclusion/exclusion criteria, noncompliance with protocol procedures, informed consent/assent process etc.).

6.15. Interim Analyses and Data Monitoring

Since this is a dose-escalation study, data will be reviewed on an ongoing basis during the study until the RP2D is determined. The purpose of these ongoing reviews is to evaluate the safety data at each dose level. A review of the data will be completed approximately after 5 patients have been treated for at least 1 cycle at a dose level without a cohort analysis.

An interim analysis will be triggered when 10 patients have been dosed at a given dose level for 1 cycle of treatment to evaluate the safety and tolerability of LY3164530. The interim analysis may include, but are not limited to, an assessment of available safety, PK, and PD data.

Enrollment may continue during the interim analysis and the dose escalation rules as outlined in [Figure JNBA.6.1](#) will continue to be followed.

Additional interim analyses may be triggered and may include, but are not limited to, assessment of available safety, PK, and PD data.

6.16. Annual Report Analyses

The following reports are needed as requested for annual reporting purposes

Clinical Investigator Brochure:

- Summary of SAE (patients on therapy).
- Summary of deaths reported (patients on therapy).
- Summary of Patient disposition.
- Summary of primary reason for treatment discontinuation.
- Summary of treatment-emergent adverse events –by CTCAE category and term.

Development Safety Update Report:

- Cumulative Subject Exposure by Age Group and Sex
- Cumulative Subject Exposure by Racial Group
- Estimated Cumulative Subject Exposure
- Subject Exposure by Gender
- Listing of Patients Who Discontinued Due to Adverse Event
- Listing of Deaths

6.17. Clinical Trial Registry Analyses

Additional analyses will be performed for the purpose of fulfilling the Clinical Trial Registry (CTR) requirements.

Analyses provided for the CTR requirements include the following:

Summary of adverse events, provided as a dataset which will be converted to an XML file. Both Serious Adverse Events (SAEs) and ‘Other’ Adverse Events are summarized: by treatment group, by MedDRA preferred term.

- An adverse event flagged as an SAE by the investigator due to meeting one or more of the standard criteria (Protocol Section 8.1.2.1) is considered ‘Serious’ whether or not it is a treatment emergent adverse event (TEAE).
- An adverse event is considered in the ‘Other’ category if it is both a TEAE and is not serious. For each Serious AE and ‘Other’ AE, for each term and treatment group, the following are provided:
 - the number of participants at risk of an event
 - the number of participants who experienced each event term
 - the number of events experienced.
- Consistent with www.ClinicalTrials.gov requirements, ‘Other’ AEs that occur in fewer than 5% of all treated patients/subjects may not be included if a 5% threshold is chosen (5% is the minimum threshold).
- AE reporting is consistent with other document disclosures for example, the CSR, manuscripts, and so forth.

A participant flow summary will also be produced. This participant flow will describe how many patients completed the study, and for those who did not, the frequency of each reason for not completing. At the time of database lock, any patient who completed one cycle of treatment or discontinued due to an adverse event and completed the required safety and full set of PK assessments during cycle 1 will be considered to have completed the study:

7. References

8. Appendices

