6.2.1. Primary Endpoint Analysis, Study Completion, and End of Trial

The primary endpoint analysis will occur after the final patient enrolled has been evaluated for at least 1 cycle. Any patient enrolled that has completed at least 1 cycle of treatment or discontinued due to an AE (during Cycle 1), and completed the required post-treatment safety assessment, will be considered to have completed the study. However, additional cycles of therapy may continue as long as the patient is receiving benefit and no criteria for discontinuation have been met. All secondary/exploratory endpoint analyses will be updated at study completion.

Both the study completion and end of trial will be the date of the last visit or last scheduled procedure for the last patient.

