7.6.1. Evaluable Patients

Patients who withdraw from the study before receiving study drug will be replaced and will not be included in the safety or efficacy assessments. Safety analyses will be conducted on all patients who have been exposed to study drug, regardless of whether they are deemed evaluable for the assessment of a dose level.

Any patient who is discontinued from the study before completing 1 cycle of LY3164530 treatment will be deemed non-evaluable for assessment of a dose level, unless they experience a DLT prior to withdrawal. However, patients who receive all doses of LY3164530, but discontinue from study drug before the end of Cycle 1, will be considered evaluable for the assessment of a dose level, provided it can be documented whether the patient experienced a DLT during Cycle 1.

If the patient is noncompliant during Cycle 1 due to reasons other than drug-related toxicity, he or she will be considered non-evaluable and may be replaced.

Patients that require a dose reduction or omission during Cycle 1 or have a dosing delay of more than 3 days for reasons other than a study drug-related AE may be deemed non-evaluable for DLT assessment.

Nonevaluable patients may be replaced to ensure that enough patients complete 1 cycle of therapy at each dose level, unless accrual to that cohort has stopped due to a DLT.

Patients who are not evaluable for PK, but who complete 1 cycle of therapy, may be replaced upon consultation with the investigator(s) and the Lilly CRP or CRS to ensure adequate PK data, unless accrual to that cohort has stopped due to a DLT.

8. Safety, Pharmacokinetic, Pharmacodynamic, and Efficacy Data Collection

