8.2.2. Samples for Drug Concentration Measurements Pharmacokinetics/Pharmacodynamics

8.2.2.1. Pharmacokinetic Samples

At the visits and times specified in [Attachment 3](#), blood samples will be collected to determine the serum concentrations of LY3164530. A maximum of 5 samples may be drawn at additional time points during the study if warranted and agreed upon between both the investigator and Lilly. Similarly, if sufficient data have been collected from other patients, a maximum of 5 samples may be removed if agreed upon between both the investigator and Lilly. Instructions for the collection and handling of blood samples will be provided by the Sponsor. The actual date and time (24-hour clock time) of each sampling will be recorded.

These samples will be analyzed at a laboratory designated by the Sponsor. Serum concentrations of LY3164530 will be assayed using a validated ELISA method.

The PK samples will be stored at a facility designated by the Sponsor.

Bioanalytical samples collected to measure LY3164530 will be retained for a maximum of 1 year following last patient visit for the study.

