Attachment 3. Protocol JNBA Pharmacokinetic and Pharmacodynamic Sampling Schedule

Pharmacokinetic and Pharmacodynamic Sampling for Schedule 1

Cycle	Day	Collection Time	PK Sampling Time	MET ECD and EGFR ECD ^a	MET and EGFR Ligands ^a	Proteomic Blood Sample ^a
1 and 2	1	Predose	X	X	X	X
	1	Mid-infusion	X			
	1	End of infusion	X	X	X	X
	1	2 hours post end of infusion	X			
	1	4 hours post end of infusion	X			
	1	6 hours post end of infusion (Cycle 1 only)	X			
	2	24 ±4 hours post-end of infusion (Cycle 1 only)	X	X	X	X
	3	Anytime during day (Cycle 1 only)	X			
	8±1	Anytime during day	X			
	15	Predose	X	X	X	X
	15	End of infusion	X	X	X	X
	15	2 hours post end of infusion (Cycle 1 only)	X			
	15	4 hours post end of infusion (Cycle 1 only)	X			
	15	6 hours post end of infusion (Cycle 1 only)	X			
	22±2	Anytime during day (Cycle 1 only)	X			
3-6	1	Predose	X	X	X	X
	1	End of infusion	X			
Follow-ups		Occurs on the day the follow-ups occur.	X	X	X	

Abbreviations: ECD = extracellular domain; EGFR = epidermal growth factor receptor; MET = mesenchymal-epithelial transition factor; PK = pharmacokinetic; V = volume of distribution.

^a Samples are requested to be taken immediately before the dose and immediately after the end of the LY3164530 infusion. Aberrations to specified sampling times will not be considered protocol deviations as long as the samples are taken and the actual sampling time is recorded. It is essential that the actual times of LY3164530 dose and samples are recorded accurately on the appropriate forms.

Pharmacokinetic and Pharmacodynamic Sampling for Schedule 2 Cycle	Day	Collection Time	PK Sampling Time	MET ECD and EGFR ECD ^a	MET and EGFR Ligands ^a	Proteomic Blood Sample ^a
1 and 2	1	Predose	X	X	X	X
	1	Mid-infusion	X			
	1	End of infusion	X	X	X	X
	1	2 hours post end of infusion	X			
	1	4 hours post end of infusion	X			
	1	6 hours post end of infusion	X			
	2	24 ±4 hours post-end of infusion	X	X	X	X
	3	Anytime during day	X			
	8	Predose	X			
	8	End of infusion	X			
	22	Predose	X	X	X	X
	22	End of infusion	X	X	X	X
	22	2 hours post end of infusion (Cycle 1 only)	X			
	22	4 hours post end of infusion (Cycle 1 only)	X			
	22	6 hours post end of infusion (Cycle 1 only)	X			
	23	24 ±4 hours post-end of infusion (Cycle 1 only)	X			
	24	Anytime during day (Cycle 1 only)	X			
3-6	1	Predose	X	X	X	X
	1	End of infusion	X			
Follow-up		Occurs on the day the follow-ups occur.	X	X	X	

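### SAP 6.17 ties study completion to a full Cycle 1 PK set, which the protocol does not require and an AE stop before the Day 15 (Schedule 1) or Day 22 (Schedule 2) dose cannot supply

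*SAP*

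**What the plan says.** Two places define when a patient has completed the study.

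- Protocol 6.2.1 counts a patient who finished at least one cycle, or who "discontinued due to an AE (during Cycle 1), and completed the required post-treatment safety assessment, will be considered to have completed the study". PK is not mentioned.
- SAP 6.17 introduces the registry output with "This participant flow will describe how many patients completed the study". Its rule has the same two routes, a finished cycle or an AE discontinuation, but the closing condition differs: patients who "completed the required safety and full set of PK assessments during cycle 1 will be considered to have completed the study".

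Two other protocol sections bear on the PK condition. Section 8.2.2.1 lets the sampling schedule change: where other patients have provided enough data, "a maximum of 5 samples may be removed if agreed upon between both the investigator and Lilly". Section 7.6.1 treats inadequate PK as a question of replacement, not of completion: "Patients who are not evaluable for PK, but who complete 1 cycle of therapy, may be replaced upon consultation".

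**The concern.** The same term has two definitions, and the SAP version works against its own AE route. That route exists so that a patient stopped early by toxicity is not recorded as having failed to complete. A full Cycle 1 PK set needs doses that such a patient never receives.

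At stake is a figure meant for a public registry. With the SAP followed as written, patients whom the protocol counts as completers would be posted as non-completers. AE discontinuations may well be more frequent at more toxic doses, so the relabelling could cluster there.

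**Working it through.** Neither document states a completer count or an expected rate of early AE discontinuation, so there is no figure to reproduce. The check compares the two rules and counts samples.

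**Step 1. How the SAP sentence parses.** It reads "any patient who completed one cycle of treatment or discontinued due to an adverse event and completed the required safety and full set", followed by the PK words, with no comma. There are two readings:

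- (a) the safety and PK condition attaches to both routes;
- (b) it attaches only to the AE route.

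The parallel protocol sentence has a comma before its safety condition, which favours (a). An AE discontinuation needs the full PK set under either reading.

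**Step 2. Scheduled Cycle 1 PK samples (Protocol Attachment 3).**

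| | Schedule 1 | Schedule 2 |
|---|---|---|
| Day 1 | 6 | 6 |
| Days 2 and 3 | 1 + 1 | 1 + 1 |
| Day 8 | 1 | 2 |
| Day 15 | 5 | none listed |
| Day 22 | 1 | 5 |
| Days 23 and 24 | none | 1 + 1 |
| Total | 15 | 17 |

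**Step 3. Samples that cannot exist without the later dose.**

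- Schedule 1, Day 15: end of infusion and 2, 4 and 6 hours after it, so 4 samples. A patient stopped before that dose can have at most 15 − 4 = 11.
- Schedule 2, Day 22: end of infusion, 2, 4 and 6 hours, and the 24-hour sample on Day 23, so 5 samples. At most 17 − 5 = 12 remain.

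If sampling ends with treatment, fewer are collected:

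- Schedule 1: a stop before Day 8 leaves 8 of 15, and a stop before Day 15 leaves 9 of 15.
- Schedule 2: a stop before Day 8 leaves 8 of 17, and a stop after the Day 8 samples but before Day 22 leaves 10 of 17.

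**Step 4. Apply both rules to one patient.** Take a patient stopped for an AE on Day 9 whose post-treatment safety assessment is done. Protocol 6.2.1 makes this patient a completer. SAP 6.17 does not, under (a) or (b).

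**Step 5. Size, on an assumed rate.** Let r be the proportion who stop for an AE before the critical dose and have the safety assessment. With n = 50, the approximate sample size in both documents, the expected number relabelled is 50r. The chance of at least one, treating patients as independent, is 1 − (1 − r)^50.

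| Assumed r | Expected number | Chance of at least one |
|---|---|---|
| 2% | 1 | 64% |
| 5% | 2.5 | 92% |
| 10% | 5 | 99.5% |
| 15% | 7.5 | over 99.9% |

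Under the protocol definition the number relabelled is zero at every r.

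**Step 6. Does the amendment explain the difference?** The summary of changes for amendment (b) lists no change to Section 6.2.1. The mismatch is therefore not a by-product of adding the weekly schedule.

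**The case against.** The strongest reply is that little depends on this label. The same participant flow must give the reasons for not completing, and SAP 6.7 separately summarises discontinuations by reason, including AE and death. An early toxicity stop stays visible. This stands, and it limits the point to the completer count.

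A reader might infer more than the documents support:

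- **That every early toxicity discontinuation becomes a non-completer.** This is too broad. SAP 6.13.2 treats a cycle as completed once all its planned treatment was received, so a patient who stops after the last Cycle 1 dose takes the finished-cycle route and can have every sample.
- **That samples removed under Protocol 8.2.2.1 break the set.** Removal must be agreed by the investigator and the sponsor. An agreed removal shrinks the required set and is not a missed sample. In principle it could even cover the samples in Step 3, but it depends on sufficient data from other patients, not on an AE.
- **That missed samples sharply lower the completion rate among patients who finished Cycle 1.** An assumed 2% miss rate per sample gives 0.98^15 = 74% with a full set on Schedule 1. That needs reading (a), a full set meaning every sample, independent misses and a miss rate that the documents do not give. Samples cluster by visit, so independence is doubtful. SAP 6.6 asks only for sufficient samples for the PK analysis, and Protocol 8.4 calls collection times targets.

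Two further cautions are fair. The SAP describes only dosing on Days 1 and 15, so the Schedule 2 result assumes that its rule is carried over to weekly dosing. The SAP sentence also ends in a colon directly before the references, so a qualifier may be missing from the available text.

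**Conclusion.** The point holds in limited form. SAP 6.17 adds a PK condition that Protocol 6.2.1 lacks. Under either reading, a patient stopped for an AE before the Day 15 dose (Schedule 1) or the Day 22 dose (Schedule 2, if the rule is applied there) cannot supply the set scheduled in Attachment 3. The SAP then labels as a non-completer someone whom the protocol counts as a completer once the safety assessment is done.

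The definitional conflict needs no assumed rate; the number of patients affected does. If the PK condition also covers patients who finished Cycle 1, a missed sample could make them non-completers too, but the documents give no basis for sizing that.

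Nothing else in the trial uses this definition: DLT evaluability, dose escalation, RP2D selection and the safety analyses are unaffected.

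**What to change.** In SAP 6.17, replace the completion sentence with the Protocol 6.2.1 definition: at least one cycle finished, or an AE discontinuation within Cycle 1, and in either case the required post-treatment safety assessment done. A comma before the safety condition, as in the protocol, removes the ambiguity over which route it governs. Report PK completeness as a separate line.

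The replacement also settles the timing of the safety assessment. The SAP wording can be read as placing it within Cycle 1, whereas Protocol 8.1.2.2.3 sets it at 28 ± 5 days after the last dose, normally after Cycle 1.

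If the sponsor does intend a PK condition, Protocol 6.2.1 should be amended to match, and the SAP should define a full set for each schedule, including how agreed removals and early AE stops are handled.

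The recommended change costs one sentence of SAP text and one extra summary line, with no new data and no effect on patients.
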